**NOTES:**

- T = Table, F = Figure, L = Listing, Y = Yes display generated.
  - Summary = Represents TF related to any summaries (i.e. descriptive statistics) of the observed raw data.
  - Individual = Represents FL related to any displays of individual participant observed raw data.
- 1 – All Subjects Enrolled population  
2 – Statistical analysis also performed for change from baseline in vital signs (pulse rate, SBP, DBP) and ECG parameters (PR interval, QTc(F) interval and heart rate)

**8.1. Extent of Exposure**

The extent of exposure to fluticasone/salmeterol [FSC], 250/50 mcg, via the DISKUS DPI during the run-in period, to FF/VI 100/25mcg, via the ELLIPTA DPI during the stabilization period, to randomised study treatment and post-treatment data will be summarized by the categories in Section 11.6.4. The number of days of post-treatment

data will also be summarized for all participants with at least one day of post-treatment data.

## 8.2. Adverse Events Analyses

Adverse events analyses including the analysis of adverse events (AEs), Serious (SAEs) and other significant AEs will be based on GSK Core Data Standards.

The CRF texts for adverse events will be coded using the Medical Dictionary for Regulatory Activities (MedDRA) and will be reported using the primary System Organ Class (SOC) and the Preferred Term.

Adverse events will be summarized and grouped by primary SOC and by adverse event (i.e., Preferred Term) within primary SOC. Results will be displayed in the order of decreasing frequency, both across primary SOC and within primary SOC. The number of participants with one or more events of any type will also be calculated. The relationship of primary SOC, Preferred Terms, and verbatim text will be listed.

The following summaries will be provided:

- AEs during screening/run-in.
- AEs during stabilization period.
- On-treatment AEs: All AEs, drug-related AEs, all SAEs, drug-related SAEs
  - Outputs will be repeated adjusted for exposure (per thousand persons years) to account for variable treatment duration
- Post-treatment AEs: All AEs, drug related AEs, all SAEs
- Post-study AEs.

Adverse events will also be summarized by gender, age, race, region, pre-study ICS dosage at screening, BMI and CV History/Risk Factor at Screening.

In addition, the on-treatment AEs and on-treatment SAEs will be presented (see Section 11.6.4 for more details on participants and reporting period included in each table):

- Up to week 24
- Up to week 36 for all participants whose EOS visit or planned EOS visit is after week 24
- Up to week 52 for all participants whose EOS visit or planned EOS visit is after week 36

In addition, common (3% or more participants in any treatment arm) on-treatment adverse will be presented. To support this, the 10 most frequent AEs in each treatment group will be presented.

## 8.3. Adverse Events of Special Interest Analyses

Adverse events of special interest have been defined as AEs which have specified areas of interest for one or more of the compounds (FF, VI and/or UMEC) or combination therapies (FF/UMEC/VI and/or FF/VI). These consist of groupings of preferred terms

based on the MedDRA dictionary version used in each reporting effort. Subgroups may be defined, based on relevant combination of preferred terms, or on Standardized MedDRA queries (SMQ).

The table below presents the special interest AE groups for FF, UMEC and VI, defined upon the release of version 21.1 of the MedDRA dictionary.

Special Interest AE Group		Special Interest AE Subgroup	PTs/SMQs for Inclusion
Cardiovascular effects*		Cardiac arrhythmia	Cardiac arrhythmia (SMQ), excluding congenital and neonatal arrhythmias
		Cardiac failure	Cardiac Failure (SMQ)
		Cardiac ischaemia	Ischaemic Heart Disease (SMQ)
		Stroke	Central nervous system haemorrhages and cerebrovascular conditions (SMQ)
		Hypertension	Hypertension (SMQ)
Pneumonia			Infective pneumonia (SMQ)
LRTI excluding infective pneumonia SMQ			Selected PTs
Decreased bone mineral density and associated fractures			Osteoporosis/Osteopenia (SMQ) Selected PTs
Hypersensitivity			Hypersensitivity (SMQ) Angioedema (SMQ) Anaphylactic reaction (SMQ)
Anticholinergic Syndrome*			Anticholinergic Syndrome SMQ
Gastrointestinal obstruction*			Gastrointestinal obstruction SMQ
Adrenal Suppression			Selected PTs
Antimuscarinic ocular effects / Corticosteroid Associated Eye Disorders		Glaucoma (antimuscarinic / corticosteroid)	Glaucoma (SMQ),
		Cataracts (corticosteroids)	Lens disorder (SMQ)
Effects on Glucose			Hyperglycaemia/new onset diabetes mellitus (SMQ)
Local steroid effects			Selected PTs
Urinary retention*			Selected PTs
Effects on potassium			Selected PTs
Tremor			Selected PTs
Asthma/Bronchospasm for Asthma-related intubations and deaths			Asthma/bronchospasm SMQ

Special Interest AE Group		Special Interest AE Subgroup	PTs/SMQs for Inclusion
Dry mouth / Drying of airway secretions*			Selected PTs (narrow and broad focus)
*: of interest for UMEC			

Adverse events of special interest will be summarized in the same manner outlined in Section 8.2 for overall AEs, and by the study population subgroups identified in Section 5.5.2.

In addition, the on-treatment AESIs will be summarized (see Section 11.6.4 for more details on participants and reporting period included in each table):

- Up to week 24
- Up to week 36 for all participants whose EOS visit or planned EOS visit is after week 24
- Up to week 52 for all participants whose EOS visit or planned EOS visit is after week 36

#### 8.4. Major Adverse Cardiac Events

Major Adverse Cardiac Events (MACE) endpoint will be analyzed using broad and narrow definitions.

The broad MACE will be defined as:

- Cardiac Ischaemia Special Interest AE Subgroup (Ischaemic Heart Disease SMQ) excluding fatalities,
- Stroke Special Interest AE Subgroup (Central Nervous System Haemorrhages and Cerebrovascular Conditions SMQ) excluding fatalities

The narrow MACE will be defined as:

- PTs of “myocardial infarction” and “acute myocardial infarction” excluding fatalities,
- Stroke Special Interest AE Subgroup (Central Nervous System Haemorrhages and Cerebrovascular Conditions SMQ) excluding fatalities

The broad and narrow MACE tables will also be provided adjusted for exposure (per thousand persons years) to account for variable treatment duration.

CV deaths will be considered in the CSR, alongside the broad and narrow MACE defined above.

## 8.5. Clinical Laboratory Analyses

On-treatment laboratory evaluations including the analyses of Chemistry laboratory tests, Hematology laboratory tests, Urinalysis, and liver function tests will be based on GSK Core Data Standards. The details of the planned displays are in [Appendix 10: List of Data Displays](#)

Laboratory values will be classified as 'Low', 'Normal', or 'High' based on the provided normal ranges.

Change from baseline values will be classified relative to the normal range as 'To Low', 'To Normal or No Change', or 'To High'. Participants who do not change categories or move from out-of-range to normal will be classified as 'To Normal or No Change'.

An 'any time post-baseline' change classification will be derived for each treatment in which participants will be counted in the 'To Low' or 'To High' categories if they reported a change from a 'Normal' baseline to a value below or above the normal range, respectively, at any on-treatment scheduled, unscheduled, or EW visit during the associated treatment. Participants who did not report a change to a value outside the normal range at any visit while taking the associated treatment will be counted in the 'To Normal or No Change' category.

## 8.6. Other Safety Analyses

The analyses of non-laboratory safety test results including ECGs and vital signs will be based on GSK Core Data Standards, unless otherwise specified.

### 8.6.1. Vital Signs

Vital signs (pulse rate, diastolic blood pressure, and systolic blood pressure) are measured at every clinic visit, starting at Visit 1, and prior to conducting spirometry.

The 'minimum post-baseline' and 'maximum post-baseline' value will be derived as the minimum and maximum on-treatment value recorded at any scheduled, unscheduled, or Early Withdrawal (EW) visit after the start of study treatment. See Section [8.6.4](#) for details on the statistical analysis of vital signs data.

### 8.6.2. ECG

The on-treatment ECG measurements of interest are QTc (F), QTc(B), heart rate, and PR interval. All ECG data present in the database will be considered valid and will be reported (even if the ECG had a technical error).

A 'maximum post-baseline' and 'minimum post-baseline' QTc (F), QTc(B), PR interval, and heart rate value will be derived as the maximum (or minimum) on-treatment value recorded at any scheduled, unscheduled, or EW visit after the start of study treatment.

Absolute and change from baseline QTc (F) values (including 'maximum post-baseline') will be categorized as detailed in Section [11.6.4](#).

See Section 8.6.4 for details on the statistical analysis of QTc (F), PR interval and heart rate data.

An ‘any time post-baseline’ ECG interpretation will be derived as the worst on-treatment interpretation recorded at a scheduled, unscheduled, or EW visit after the start of study treatment. The order of severity from worst to best for ECG interpretation is: abnormal, normal, unable to evaluate.

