7.5.6. Electrocardiogram (ECG)

All sites will use standardised ECG equipment provided by a centralized external vendor. At the Screening Visit (Visit 1), a single 12-lead ECG and rhythm strip will be recorded after the measurement of vital signs but before performing the pre-bronchodilator spirometry assessment. At the post-randomization visits, a single 12-lead ECG and rhythm strip will be recorded 15 to 45 minutes after the administration of study treatment. Recordings will be made at the time-points defined in the Time and Events table (Section [7.1](#)). All ECG measurements will be made with the subject in a supine position having rested in this position for approximately 5 minutes before each reading.

For subjects who meet the QTc, protocol defined stopping criteria, triplicate ECGs (over a brief period of time) should be performed (Section 5.6.4).

The Investigator, a designated sub-Investigator or other appropriately trained site personnel will be responsible for performing each 12-lead ECG. The Investigator must provide his/her dated signature on the original paper tracing, attesting to the authenticity of the ECG machine interpretation.

All ECGs will be electronically transmitted to an independent cardiologist and evaluated. The independent cardiologist, blinded to treatment assignment, will be responsible for providing measurements of heart rate, QT intervals and an interpretation of all ECGs collected in this study. A hard copy of these results will be sent to the Investigator. The Investigator must provide his/her dated signature on the confirmed report, attesting to his/her review of the independent cardiologist's assessment.

Details of the cardiac monitoring procedures will be provided by the centralized cardiology service provider.

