## 5.2. Baseline Definition & Derivations

For clinic FEV1, the Baseline value is the last acceptable/borderline acceptable pre-dose FEV1 prior to randomized treatment start date (either from pre-dose at Day 1 or pre-bronchodilator at Enrolment Visit or at an unscheduled visit which occurs between the Enrolment Visit and Day 1).

For ACQ, SGRQ, and AQLQ, baseline value for each endpoint is the derived value based on the questionnaire administered at the randomization visit.

For the safety assessments of clinical laboratory, vital signs, and ECGs, the baseline value is the latest value recorded prior to first dose, including pre-dose unscheduled visits.

For diary data the baseline is the average value over the last 14 days prior to randomized treatment start (for more details see Section 5.3.2). If fewer than 7 days of data over the baseline period are available, the baseline value will be set as missing.

If time is not collected, Day 1 clinic assessments (or Day 1 AM diary assessments) are assumed to be taken prior to first dose and used in the derivation for baseline.

All baselines will be referred to as ‘Baseline’ in the summary outputs.

Parameter	Study Assessments Considered as Baseline	
Clinic Assessments		
	Screening	Day 1 (Pre-Dose)
Efficacy		
Trough FEV 1 , FEV 1 3h post study treatment		X*
ACQ-5, ACQ-6, ACQ-7, SGRQ, AQLQ, Global Assessment of Severity		X
Safety		
Clinical Laboratory (incl. total serum IgE and FeNO) †	X	
ECGs†	X	
Vital signs†		X
Diary Assessments		
	Baseline Period	
Efficacy		
Home Daily Trough FEV 1 , Home Daily AM PEF	Last 14 AM assessments during the stabilisation period, including AM assessment on the day of first treatment, prior	

Parameter	Study Assessments Considered as Baseline
	to first dose (i.e., treatment start date per protocol)
Home Daily PM FEV 1 , Home Daily PM PEF	Last 14 PM assessments immediately preceding first treatment during the stabilisation period
%Symptom free days, % rescue medication free days, daily rescue medication use	Last 14 days during the stabilisation period, including AM assessments on the day of treatment i.e., treatment start date per protocol).
E-RS total score and domain scores	Last 14 PM assessments immediately preceding first treatment date during the stabilisation period

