Up to 24 weeks	
 
If participants planned EOS visit is week 24: up to last treatment date +1
 
If participants planned EOS visit is later than week 24 use data up to the minimum (169, last treatment date+1)
 

Up to 36 weeks	
 
If participants planned EOS visit is week 24: exclude from summary table
 
If participants planned EOS visit is week 36: up to last treatment date +1
 
If participants planned EOS visit is week 52 use data up to the minimum (253, last treatment date+1)
 

Up to 52 weeks	
 
If participants planned EOS visit is week 24: exclude from summary table
 
If participants planned EOS visit is week 36: exclude from summary table
 
If participants planned EOS visit is week 52 use data up to last treatment date+1
 

Maximum/Minimum Post-Baseline and Worst-Case Post-Baseline	
Definition	Reporting Details
Maximum post-baseline	Maximum value over all on-treatment timepoints
Minimum post-baseline (Assessments that do not have a lower limit = 0)	Minimum value over all on-treatment timepoints
Worst case post-baseline (ECG findings)	
 
'Abnormal' if any on-treatment assessment is evaluated as 'Abnormal'
 
'Unable to evaluate' if all on-treatment assessments are 'Unable to evaluate'
 
'Normal' if any on-treatment assessment is evaluated as 'Normal' and there are no on-treatment assessments evaluated as 'Abnormal'
 

**Note:** Assessment of minimum/maximum/worst-case post-baseline will include on-treatment data from scheduled, unscheduled and study discontinuation visits (if applicable).

Laboratory Parameters

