
 
• Non-quantifiable laboratory results will be treated as missing in summary displays. However, the results will be listed as received (e.g. '<x' or '>x').
 
• An 'any visit post-baseline' classification will be derived, in which participants will be counted in the 'low' and 'high' categories if they reported a low or high value at any scheduled or unscheduled on-treatment visit during the study.
 
• Change from baseline values will be classified relative to the normal range as 'to low', 'to normal or no change' or 'to high'. Participants who do not change categories or move from out-of-range to normal will be classified as 'to normal or no change'.
 
• An 'any visit post-baseline' change classification will be derived, in which participants will be counted in the 'to low' and 'to high' categories if they reported a change from a 'normal' baseline to a value below or above the normal range (respectively) at any on-treatment scheduled or unscheduled visit during the study. Participants who did not report a change to a value outside the normal range at any visit after the start of study treatment will be counted in the 'to normal or no change' category.
 

Multiple Measurements for Post-Baseline Visits for Safety

 
• Participants having both high and low values relative to normal ranges at post-baseline on-treatment visits for safety parameters will be counted in both the high and low categories of the "any visit post-baseline" row of related summary tables.
 

Urinalysis

Potential Clinical Importance is defined as an increase in Protein or Occult Blood post-baseline relative to Baseline (Screening), or if microscopy is performed.

ECG			
QTcF and QTcF change from baseline results will be reported in categories as below			
ECG Parameter	Units	Ranges	
		Lower	Upper
Absolute			
Absolute QTcF Interval	msec	0	≤ 450
		> 450	≤ 480
		> 480	≤ 500
		> 500	≤ 530
		> 530	
Change from Baseline			
Change from Baseline QTcF	msec		≤ -60
		> -60	≤ -30
		> -30	≤ 0
		> 0	≤ 30
		> 30	≤ 60
		> 60	

Pneumonia (AESI)
Pneumonia Event Rate

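### The SAP counts ECGs with a technical error as valid, so an unreliable QTcF can enter the baseline, the maxima, the outlier categories and the Week 24 models

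*SAP*

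**What the plan says.** SAP 8.6.2 (ECG) sets the rule for data quality: "All ECG data present in the database will be considered valid and will be reported (even if the ECG had a technical error". It then defines the post-baseline extremes for QTcF, QTcB, PR interval and heart rate; each "will be derived as the maximum (or minimum) on-treatment value recorded at any scheduled, unscheduled, or EW visit after the start of study treatment". SAP 11.6.4 (Safety) repeats the visit rule without a quality condition: "Assessment of minimum/maximum/worst-case post-baseline will include on-treatment data from scheduled, unscheduled and study discontinuation visits".

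These values are used in four places:

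- **Outlier bands.** SAP 8.6.2 categorizes absolute QTcF and change from baseline, and includes the maximum. SAP 11.6.4 gives the bands; the top ones are above 500 to 530 msec, above 530 msec, and a change above 60 msec.
- **Plots of the maximum.** Figures 3.14 and 3.15 show the distribution of maximum QTcF and of its change from baseline.
- **Models.** SAP 8.6.4.1 fits repeated-measures models to on-treatment heart rate, PR interval and QTcF up to Week 24 (Tables 3.86 to 3.88).
- **Baseline.** SAP 5.2 takes the latest ECG before first dose, including unscheduled visits. The Time and Events table (Protocol 7.1) schedules one pre-randomization ECG, at Visit 1, and Protocol 7.5.6 makes it a single tracing.

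Protocol 7.5.6 also sends every ECG to an independent cardiologist, blinded to treatment, who "will be responsible for providing measurements of heart rate, QT intervals and an interpretation of all ECGs collected in this study".

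**The concern.** A maximum is the summary most easily moved by one bad value, and QTcF outlier counts are normally small, so a few unreliable tracings could make up much of what is counted. A faulty baseline does further damage, because it shifts every later change for that participant: too short and it creates a false rise, too long and it hides a real one. ECG measurements are a listed safety endpoint (Protocol 3), and cardiovascular effects of UMEC and VI are the first risk in Protocol 4.6.1, so these displays should be as clean as the data allow.

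The SAP is also uneven in how it treats quality. For ECG interpretations, a tracing that could not be evaluated ranks last in severity, so any readable tracing overrides it. The numeric QTcF has no matching rule. For clinic spirometry, "the Baseline value is the last acceptable/borderline acceptable pre-dose FEV"₁ value, so a quality condition is applied there.

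**Working it through.** **What the text establishes.** SAP 8.6.2 admits all tracings, SAP 11.6.4 repeats the visit rule unfiltered, and the categories, figures and models draw on the same data. A search of both documents for a quality exclusion or a sensitivity display on ECGs finds neither. The path into the results is therefore stated in the plan. How often it is used is not: there is no figure in the plan to reproduce, and everything numerical below is illustration.

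**Inputs from the documents.** 375 participants per arm (Protocol 9.2.1). On-treatment scheduled ECGs per participant: k = 2 if the end-of-study visit is Week 24 (Weeks 4 and 24), k = 3 if it is Week 36 or 52 (Protocol 7.1 and 4.2).

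**Assumed inputs.** Error rate per tracing p; within-person reading SD 12 msec; no drug effect.

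*Step 1: participants per arm with at least one affected on-treatment ECG*, 375 × [1 − (1 − p)^k]:

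| p | k = 2 | k = 3 |
|---|---|---|
| 0.1% | 0.75 | 1.12 |
| 0.5% | 3.74 | 5.60 |
| 1% | 7.46 | 11.14 |
| 2% | 14.85 | 22.05 |

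*Step 2: false changes above 60 msec, symmetric error.* By simulation, change = maximum of the k on-treatment readings minus baseline. Each tracing, baseline included, has probability p of an added zero-mean error with SD 30 or 50 msec. Participants per arm = 375 × probability.

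| p | k = 2: probability (SD 30 / 50) | per arm | k = 3: probability (SD 30 / 50) | per arm |
|---|---|---|---|---|
| 0 | 0.04% | 0.15 | 0.06% | 0.23 |
| 1% | 0.18% / 0.45% | 0.7 / 1.7 | 0.25% / 0.61% | 0.9 / 2.3 |
| 2% | 0.32% / 0.85% | 1.2 / 3.2 | 0.44% / 1.17% | 1.7 / 4.4 |

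With k = 3, the ratio to the clean background runs from 0.25 / 0.06, about 4, to 1.17 / 0.06, about 20.

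*Step 3: a harsher, one-sided error.* Assume mean QTcF 410 msec, between-person SD 18, and +100 msec on each affected on-treatment tracing. At p = 1%, 5.2 (k = 2) to 7.6 (k = 3) participants per arm exceed 500 msec, against 0.01 to 0.02 with clean data. The mean QTcF moves by only about 1 msec. The extremes are sensitive to this rule; the means are not.

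*Step 4: masking.* A baseline too long by e msec lowers every later change by e. With e = 30, a real rise must exceed 60 + 30 = 90 msec before it is counted in the top change band.

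**The case against.** The strongest reply is that a technical error need not mean a wrong QTcF. Neither document defines the term, the intervals are supplied by a blinded cardiologist, and an unreadable tracing may leave no number in the database at all. That stands: a reader might infer that artefacts do enter the tables, but the documents show only that they can. It also means that the error rates and error sizes above are assumptions.

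A reader might also infer that the rule biases the comparison or conceals a UMEC effect. The documents do not support this. The trial is double-blind and the reading is blinded, so errors should fall alike across arms. Similar spurious counts in each arm shrink a ratio and add noise, but leave the difference in proportions roughly unchanged, and a shared shift largely cancels in the models. Nor are the outlier counts shown to be the main cardiac result: they are descriptive, no ECG display has headline priority in SAP 11.10, and cardiovascular events of special interest and MACE are analysed separately.

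There are partial safeguards. An unscheduled repeat before first dose replaces a faulty screening ECG. Exclusion criterion 8 would tend to remove participants with an extreme screening QTcF. Triplicates are called for when a QTc stopping criterion is met, but the SAP does not say that they are averaged before the maximum is taken, so a faulty first value can survive. Individual stopping decisions follow Protocol 5.6.4 and do not depend on this rule.

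Finally, keeping every safety value is a defensible convention because it prevents selective deletion, and the spirometry contrast is limited because that condition serves an effort-dependent efficacy test. Both points argue for keeping the all-ECG display, not for having it alone.

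**Conclusion.** The point holds as a modest, inexpensive improvement. The SAP states in terms that technically faulty ECGs count, and it carries any number they hold into the baseline, extremes, categories and models with nothing to show how much depends on them. The expected consequence is noisier outlier counts and false single-participant signals, or a masked change where the baseline is faulty. It is not a directional bias between arms.

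The size is unknown. Under the symmetric assumptions at a 1% to 2% error rate, roughly 0.7 to 4.4 false changes above 60 msec would appear per arm of 375, against 0.15 to 0.23 with clean tracings. These figures rest on an assumed error rate, error SD and reading SD, and on the central reading not having already removed or corrected the affected values. If it has, the effect could be close to nil.

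**What to change.** Amend SAP 8.6.2 before unblinding:

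1. Use the blinded central reading to identify ECGs whose intervals could not be measured reliably. The sponsor should first confirm that a technical-error or not-evaluable flag is held; the SAP's wording implies one but neither document describes it.
2. Keep every flagged ECG in the listings and report the number flagged by arm.
3. Derive the baseline, the maxima and minima, the QTcF categories and the models in Tables 3.86 to 3.88 from evaluable ECGs, using a repeat tracing where one exists.
4. Show the all-ECG version alongside. Equally acceptable is to leave all-ECG as the main display and add the evaluable-only version as a sensitivity display.

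Fixing the rule on blinded readings answers the worry about selective removal. The cost is a short change of text, one filter if the flag exists, and one extra set of displays. A few values drop out of one set of tables, and a participant whose only pre-dose ECG is flagged would have no change from baseline there; all remain in the listings and the all-ECG version.
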